4.3 SECONDARY ENDPOINT(S) ANALYSIS

The type I error-controlled secondary endpoints of this study will be tested hierarchically according to the following pre-specified and fixed order of endpoints only if the primary endpoint, PFS, is statistically significant at the primary PFS analysis:

1. Overall survival (OS)
2. Objective response rate (ORR)
3. Best overall objective response rate (BOR)
4. Clinical benefit rate (CBR)
5. Time to confirmed deterioration (TTCD) in pain
6. TTCD in physical functioning (PF)
7. TTCD in role functioning (RF)
8. TTCD in Global Health Status/Quality of Life (GHS/QoL).

To adjust for multiple statistical testing of the key secondary efficacy endpoints, thereby controlling the overall type I error rate at a two-sided significance level of 5%, the fixed-sequence testing procedure will be used, where each subsequent endpoint will be formally tested at a two-sided significance level of 0.05 only if all previously tested hypotheses are statistically significant.

The primary efficacy analysis population is used for all secondary endpoints unless otherwise specified.

4.3.1 Key Secondary Endpoint

4.3.1.1 Overall Survival

The secondary comparison of interest is the hazard ratio of OS.

OS is defined as the time from randomization to death from any cause. Data for patients who are alive at the time of the analysis data cutoff will be censored at the last date they

were known to be alive. Data from patients without post-baseline information will be censored at the date of randomization.

Analysis methodology is as outlined for the primary endpoint, PFS.

An interim analysis of OS will be performed at the time of the primary analysis of PFS. In addition to the fixed sequence testing approach described before, a group-sequential design (Lan-DeMets with O'Brien-Fleming stopping boundaries) will be used to control the overall type I error rate ([Lan and DeMets 1983](#)) for the OS interim analysis and a final (event-driven, after approximately 153 OS events) analysis of OS.

The median OS in the control arm is assumed to be 35 months and the median OS in the experimental treatment arm is assumed to be 50 months, equating to a hazard ratio of 0.7. At the time of the primary PFS analysis, on the basis of the above assumptions, 105 OS events are expected to have occurred and 153 OS events for the final analysis of OS are expected to have occurred 19 months later. With the above assumptions, the cumulative power at the interim and final OS analysis is 25% and 59%, respectively. This statistical analysis plan for OS has been designed to provide appropriate OS information and maturity to support the primary PFS endpoint. However, if appropriate, additional exploratory analyses of OS may be conducted after the final analysis at time points defined through study milestones such as Health Authority interactions.

Following the estimand framework ([ICH 2020](#)), the attributes of the estimand for the secondary endpoint are defined as follows:

- **Population:** As defined for the primary estimand in Section [4.2.1](#)
- **Variable:** OS defined as time from randomization to death from any cause.
- **Treatment:** As defined for the primary estimand in Section [4.2.1](#)
- **Intercurrent events and Handling strategy:**
 - Start of non-protocol anticancer therapy prior to OS. Following treatment policy, the ICE will be ignored.
 - Early discontinuation from study treatment for any reason prior to an OS event. Following treatment policy, the ICE will be ignored.
- **Population-level summary:** Hazard ratio for OS.

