4.6.2 Patient Discontinuation from the Study

Patients have the right to voluntarily withdraw from the study at any time for any reason. In addition, the investigator has the right to withdraw a patient from the study at any time.

Reasons for withdrawal from the study may include, but are not limited to, the following:

- Patient withdrawal of consent
- Loss to follow-up
- Patient non-compliance, defined as failure to comply with protocol requirements as determined by the investigator or Sponsor
- Study termination or site closure

Note that all patients are to be followed for survival following the discontinuation of study treatment, except in the cases noted above.

Every effort should be made to obtain a reason for patient discontinuation from the study. The primary reason for discontinuation from the study should be documented on the appropriate eCRF. Patients will not be followed for any reason after consent has been withdrawn. Patients who withdraw from the study will not be replaced.

If a patient withdraws from the study, the study staff may use a public information source (e.g., county records, published obituaries, etc.), in accordance with local regulations, to obtain information about survival status.

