6.4.2.1 Overall Survival

Overall survival after randomization is defined as the time from randomization to death from any cause. Data for patients who are alive at the time of the analysis data cutoff will be censored at the last date they were known to be alive. Data from patients without post-baseline information will be censored at the date of randomization.

Analysis methodology is as outlined for the primary endpoint, PFS.

An interim analysis of OS will be performed at the time of the primary analysis of PFS. In addition to the fixed sequence testing approach described before, a group-sequential design (Lan-DeMets with O'Brien-Fleming stopping boundaries) will be used to control the overall type I error rate (Lan and DeMets 1983) for OS interim and final analyses, which will occur approximately 19 months later, as defined in Section 6.9.1.1.

The median OS in the control arm is assumed to be 35 months and the expected median OS in the experimental treatment arm is assumed to be 50 months, equating to a hazard ratio of 0.7. At the time of the primary PFS analysis, on the basis of the above assumptions, 105 OS events are expected to have occurred. 153 OS events are expected to have occurred at the final analysis, which will occur approximately 19 months later.

Of note, the endpoint of OS may not be met at the time of the *final* analysis because *the data may not be mature*. Therefore, additional *exploratory* analyses of OS *may be* conducted after the *final* analysis at timepoints defined through study milestones, such as Health Authority interactions. *Please refer to the SAP for further details.*

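### OS counts deaths found in public sources after study withdrawal but gives no matching follow-up time to withdrawn patients not found dead

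*SAP*

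**What the plan says.** The event is broad. SAP 4.3.1.1 states "OS is defined as the time from randomization to death from any cause", with no limit on how the death is learned and no cut at study withdrawal. The SAP censoring rule begins "Data for patients who are alive at the time of the analysis data cutoff will be censored at the last date they"; Protocol 6.4.2.1 has the same rule, under which such patients "will be censored at the last date they were known to be alive".

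Protocol 4.6.2 governs what is learned after withdrawal. On consent it says "Patients will not be followed for any reason after consent has been withdrawn". For patients who leave the study it then adds: "the study staff may use a public information source (e.g., county records, published obituaries, etc". The stated aim of that search is "to obtain information about survival status", and local regulations apply. The search is optional. Nothing fixes when it is done, for which patients, or what is recorded when it finds nothing.

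The OS estimand lists two intercurrent events: non-protocol anticancer therapy and early discontinuation of study treatment. Study withdrawal is not addressed. SAP 4.2.3 and 4.2.4 specify sensitivity and supplementary analyses for PFS; there are none for OS.

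**The concern.** Read together, these sections make post-withdrawal follow-up depend on the outcome. Suppose two patients withdraw at month 10. One is found by obituary to have died at month 30 and is an event at month 30. The other is alive at month 40 and has no new known-alive date, so is censored at month 10, although a death at any time up to month 40 could have counted. Between months 10 and 30 the risk set holds the patient who will die and not the one who survives. The numerator gains deaths, while the denominator lacks the living patients' time.

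Estimated survival is then too low in any arm with withdrawals. If the arms differ in withdrawal or search yield, the hazard ratio is biased too. OS is first in the fixed sequence of SAP 4.3, which is described as "controlling the overall type I error rate at a two-sided significance level of 5"%, and it gates the seven endpoints after it. Its final power is only 59%, so there is little room for distortion in either direction.

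**Working it through.** **Inputs from the documents.** 320 patients randomized 1:1 over 43 months; OS medians 35 and 50 months (HR 0.70); looks at months 50 and 69 with 105 and 153 deaths; boundaries p 0.0132 (HR 0.615) and 0.0460 (HR 0.724); power 25% and 59%. A 15% annual dropout is stated for PFS sizing. No OS withdrawal rate and no search yield are given, so both are assumptions below.

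**Step 1: reproduce the plan.** The drift is (√d/2)·|ln HR|.
- Final: (√153/2)(0.357) = 2.21. Two-sided 0.0460 gives z = 1.995 and a boundary of exp(−2×1.995/√153) = 0.724. The two-look Lan-DeMets O'Brien-Fleming calculation gives 59.1% cumulative power (stated 59%).
- Interim: (√105/2)(0.357) = 1.83, with power 26.1% (stated 25%).

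The plan's figures are reproduced closely.

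**Step 2: what loss rate do 105/153 deaths imply?** For each arm, take λ = ln 2/median, ω = −ln(1−w)/12 for annual loss w, and g = λ+ω. With uniform accrual, the expected deaths by month τ are

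160·(λ/g)·[1 − (e^(−g(τ−43)) − e^(−gτ))/(43g)].

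Summed over the arms:

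| Annual loss | Month 50 | Month 69 |
|---|---|---|
| 0% | 117 | 172 |
| 5% | 110 | 157 |
| 7.5% | 106 | 150 |
| 10% | 103 | 144 |
| 15% | 97 | 131 |
| Plan | 105 | 153 |

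The plan fits roughly 6-9% per year. At 5-10%, a complete search would add about 172−157 = 15 to 172−144 = 28 deaths to a month-69 count.

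**Step 3: compare conventions by simulation.** OS and withdrawal are exponential and independent, the cutoff is month 69, and a Cox model is fitted to a large sample. The conventions are (a) events and censoring both stop at withdrawal; (b) the documents' rule; (c) found deaths count and all other withdrawn patients are carried to the cutoff.

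Equal withdrawal, convention (b), medians in months (true 35/50):

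| Withdrawal per year | All deaths found | Half found |
|---|---|---|
| 5% | 33.6/46.2 | 34.1/47.7 |
| 7.5% | about 33/45 | about 33.5/47 |
| 10% | 32.0/43.6 | 33.4/46.1 |

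The hazard ratio under (b) is about 0.70-0.71, and null type I error stays near 5%.

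Unequal withdrawal, hazard ratio (true 0.70):

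| Control / inavolisib | (a) | (b), all found | (b), half found | (c), half found |
|---|---|---|---|---|
| 5% / 10% | 0.70 | 0.75-0.76 | 0.73 | 0.67 |
| 10% / 5% | 0.70 | 0.66-0.67 | 0.69 | 0.76 |

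**Step 4: effect on the decision.** These are trials of 320 patients with 80% of deaths found and a single look at |Z| > 1.96. False positives favouring inavolisib are 1.3% when inavolisib loses more patients (5%/10%) and 5.3% when control does (10%/5%), against a nominal 2.5%. Power is 46% and 73%, against 57% and 59% under (a).

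**Step 5: withdrawal related to prognosis.** Double the death hazard after withdrawal (an assumption) and find half the deaths. At 7.5% in both arms the true medians are about 32/45; rule (b) reads about 33/45 and (a) reads about 35/50. With modestly more withdrawal on inavolisib (6% against 9%), the true hazard ratio is about 0.73-0.74; (b) gives 0.74 and (a) gives 0.70.

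**The case against.** The strongest reply is that the asymmetry is inferred: no sentence states it. The search is for survival status, not deaths only, and a source that dates a patient as alive would advance the censoring date under the rule as written. That is right as far as it goes. But the named examples mainly report deaths, a search that finds nothing supplies no alive date, and no dated status is required.

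The trial is also double-blind, and Protocol 3.3.5 expects this to limit dropout. With equal withdrawal the tested quantity, the hazard ratio, hardly moves. This stands, and it limits the point: the hazard ratio result needs a difference between arms that the documents neither state nor rule out.

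A reader might take the 15% annual dropout as the withdrawal rate and infer much larger errors in the medians. The documents do not support that: the figure belongs to the PFS sizing, and 15% would give about 97/131 deaths, not 105/153. A reader might also infer that the rule works against inavolisib, or inflates type I error generally. The direction depends on which arm loses more patients, and under equal loss type I error is about 5%.

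Finally, ending OS at withdrawal may seem the obvious replacement. It discards known deaths from a death-from-any-cause endpoint, and Step 5 shows it can be the more biased choice when withdrawn patients do worse.

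**Conclusion.** The point holds in a limited form. The OS rule, combined with an optional search of mainly death-reporting sources, adds late events without the survivors' matching time, and no planned analysis exposes this. At the loss rate implied by the plan's own event counts, medians are understated by about 2 months in control and 5 months in the inavolisib arm if every death is found (35−33 and 50−45), and by about 1.5 and 3 months if half are found. The hazard ratio is materially affected only if withdrawal or search yield differs by arm. A 5%/10% split with a complete search moves its expected value across the 0.724 boundary; the reverse split moves it further below.

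These sizes rest on assumed withdrawal rates and search yields, exponential times and, except in Step 5, withdrawal unrelated to prognosis. The implied 6-9% is total OS loss; the share that would be searched is unknown. This is a worthwhile, inexpensive improvement and not a reason to change the main OS definition.

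**What to change.** Keep the main OS definition. In SAP 4.3.1.1, with a matching edit to Protocol 4.6.2, specify the following.

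- State that deaths found in public sources count as OS events.
- At each OS cutoff, seek public-source vital status in the same way for all withdrawn patients in both arms, where local law allows.
- Record the source, the search date and any dated alive status.
- Advance the censoring date only when the source gives a dated alive status or is a registry complete for deaths. Carrying everyone to the cutoff after an incomplete search creates its own bias (convention (c) in Step 3).
- Add an OS sensitivity analysis in which events and censoring both end at study withdrawal.
- Report withdrawals and public-source deaths by arm.

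The cost is a small search and data-entry burden, a minor protocol edit (the SAP does not govern site follow-up) and one extra analysis. That analysis assumes withdrawal is unrelated to prognosis, so it should sit beside the main analysis and not replace it.

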4.3.1.2 Objective Response Rate

Patients not meeting the criteria for ORR, including patients with no response assessments (for whatever reason) will be considered non-responders.

Following the estimand framework ([ICH 2020](#)), the attributes of the estimand for the secondary endpoint are defined as follows:

- **Population:** As defined for the primary estimand in Section [4.2.1](#).

- **Variable:** ORR, defined as the proportion of patients with a CR or PR on two consecutive occasions ≥ 4 weeks apart, as determined by the investigator according to RECIST v1.1.
- **Treatment:** As defined for the primary estimand in Section 4.2.1
- **Intercurrent events and Handling strategy:**
 - As defined for the primary estimand in Section 4.2.1
 - **ICE Handling Strategy:** Following treatment policy, all the ICE's will be ignored and tumor assessment data collected after the ICE will be included in the ORR analysis.
- **Population-level summary:** Difference in proportion

An estimate of the response rate and its 95% CI will be calculated using the Blyth-Still-Casella method for each treatment arm. Response rates in the treatment arms will be compared using the stratified Mantel-Haenszel test. Confidence intervals for the difference in ORRs between the two arms will be determined using the normal approximation to the binomial distribution.

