6.4.2.2 Objective Response Rate

Objective response rate is defined as the proportion of patients with a CR and/or PR on at least two consecutive occasions ≥ 4 weeks apart, according to RECIST v1.1. Patients who did not achieve a confirmed response and patients with no response assessments (for whatever reason) will be considered non-responders.

An estimate of the response rate and its 95% CI will be calculated using the Blyth-Still-Casella method for each treatment arm. Response rates in the treatment arms will be compared using the stratified Mantel-Haenszel test. Confidence intervals for the difference in objective response rates between the two arms will be determined using the normal approximation to the binomial distribution.

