1.2.1 Treatment Assignment and Blinding

This is a randomized, double-blind study. After initial written informed consent has been obtained, all screening procedures and assessments have been completed, and eligibility has been established for a patient, the study site will obtain the patient's identification number and treatment assignment from an interactive voice or web-based response system (IxRS).

Patients will be randomly assigned to one of two treatment arms: inavolisib plus palbociclib and fulvestrant or placebo plus palbociclib and fulvestrant. Randomization will occur in a 1:1 ratio using a permuted-block randomization method to ensure a balanced assignment to each treatment arm.

Randomization will be stratified according to the following factors:

- Visceral disease (yes or no)
- Endocrine resistance (primary or secondary according to ESMO ABC4 guidelines [[Cardoso et al. 2018](#)])
- Geographic region (North America/Western Europe, Asia, Other).

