4.3.1.3 Best Overall Response

Patients not meeting the criteria for BOR, including patients with no response assessments (for whatever reason) will be considered non-responders.

Following the estimand framework (ICH 2020), the attributes of the estimand for the secondary endpoint are defined as follows:

- **Population:** As defined for the primary estimand in Section 4.2.1.
- **Variable:** BOR, defined as the proportion of patients with a CR or PR, as determined by the investigator according to RECIST v1.1.
- **Treatment:** As defined for the primary estimand in Section 4.2.1
- **Intercurrent events and Handling strategy:**
 - As defined for the primary estimand in Section 4.2.1
 - **ICE Handling Strategy:** Following treatment policy, all the ICE's will be ignored and tumor assessment data collected after the ICE will be included in the BOR analysis.
- **Population-level summary:** Difference in proportion

Analysis methodology is as outlined for ORR.

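### For ORR, BOR and CBR the test is stratified but the confidence interval for the difference names no strata, so the two can disagree near p = 0.05

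*SAP*

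**What the plan says.** SAP 4.3.1.2 gives two methods for one comparison. For the test: "Response rates in the treatment arms will be compared using the stratified Mantel-Haenszel test". For the interval: "Confidence intervals for the difference in ORRs between the two arms will be determined using the normal approximation to the binomial distribution". Protocol 6.4.2.2 has the same interval, stating that the "difference in objective response rates between the two arms will be determined using the normal approximation to the binomial distribution". Neither document mentions strata or weights for it.

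The population-level summary for ORR is "Difference in proportion", so this is the interval for the estimand. SAP 4.3.1.3 carries the approach to BOR ("Analysis methodology is as outlined for ORR"), and SAP 4.3.1.4 does the same for CBR.

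All three endpoints are in the fixed testing sequence of SAP 4.3, after PFS and OS, where "each subsequent endpoint will be formally tested at a two-sided significance level of 0.05 only if all previously tested hypotheses are statistically significant".

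For PFS, SAP 4.2.2 pairs the stratified log-rank test with a stratified Cox hazard ratio that uses the IxRS randomization factors. The unstratified result is a sensitivity analysis. OS follows PFS.

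**The concern.** Randomization is stratified by visceral disease, endocrine resistance and region (SAP 1.2.1). The test for ORR uses stratification. As written, the reported interval does not, so the p-value and the interval rest on different variances.

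Two things follow. Near 0.05 the trial could report a significant result on a type I error-controlled endpoint beside an interval that includes zero, or the reverse. And if the strata predict response, the unstratified variance counts between-stratum variation that stratified randomization has already balanced out, so the interval is too wide.

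The interval also matters when no formal ORR test takes place. If OS is not significant, the sequence stops, and the difference with its interval becomes the main evidence on response.

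**Working it through.** **The plan's own figures.** The documents give no planning rate, power or interval width for ORR, BOR or CBR, so there is no figure on this point to reproduce. The figure that sizes the trial does reproduce (SAP 2.2: hazard ratio 0.65, two-sided 0.05, 85% power): 4 × (1.960 + 1.036)² / (ln 0.65)² = 193.5, rounded up to the stated 194 PFS events.

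**Step 1: the point estimate.** Mantel-Haenszel weights for a risk difference are n1·n0/(n1 + n0) in each stratum. With 1:1 allocation within strata this is n/4, proportional to stratum size, so the weighted difference equals the crude difference. It does so exactly under perfect balance, and nearly so with permuted blocks. Only the variance differs.

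**Step 2: a worked example.** The data are assumed: two strata of 80 per arm, with responders 16 v 8 and 44 v 36.

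- Crude rates: 60/160 = 0.375 and 44/160 = 0.275; difference 0.100.
- Stratified test, without continuity correction (the SAP mentions none). Observed minus expected is 16 − 12 = 4 and 44 − 40 = 4. Variances are 80·80·24·136/(160²·159) = 5.132 and 80·80·80·80/(160²·159) = 10.063. Chi-square = 8²/15.195 = 4.21, p = 0.040.
- Unstratified interval: SE = √[(0.375·0.625 + 0.275·0.725)/160] = 0.0521; 95% CI −0.2 to 20.2 points, which includes zero.
- Stratified interval: variance = ¼[(0.2·0.8 + 0.1·0.9)/80 + (0.55·0.45 + 0.45·0.55)/80] = 0.002328 (the Sato variance gives the same value here); SE = 0.0483; 95% CI 0.5 to 19.5 points, which excludes zero.
- Ratio of widths: 0.0521/0.0483 = 1.08.

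With a continuity correction the statistic would be (8 − 0.5)²/15.195 = 3.70, p = 0.054, so this example depends on the uncorrected test.

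**Step 3: how often.** This was simulated with 20,000 trials per scenario. From the documents: 320 patients, 1:1 permuted blocks, 2 × 2 × 3 = 12 strata, two-sided 0.05. Assumed: block size 4; stratum shares; a common odds ratio across strata; control rate 19%, 25%, 40% or 67%; true difference 0 to 20 points; SD of the stratum effect on the logit scale 0 (none), 0.5 (moderate) or 1.0 (strong). The 19% and 67% are the ORR and CBR on palbociclib plus fulvestrant in the phase III trial described in Protocol 1.1.

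One scenario in detail (control rate 25%, difference 12 points):

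| Stratum effect | Test and unstratified CI disagree | of which p < 0.05, CI includes 0 | of which p ≥ 0.05, CI excludes 0 | Test and stratified CI disagree | Width, unstratified / stratified | SD of estimate, crude / stratified | Coverage, unstratified |
|---|---|---|---|---|---|---|---|
| None | 1.5% | 0.5% | 1.0% | 0.6% | 1.00 | 0.0513 / 0.0514 | 94.9% |
| Moderate | 2.3% | 1.8% | 0.5% | 0.7% | 1.02 | 0.0500 / 0.0500 | 95.5% |
| Strong | 6.0% | 5.9% | 0.1% | 0.6% | 1.09 | 0.0469 / 0.0468 | 96.8% |

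Across all scenarios with a true difference, disagreement is 0.4-1.8% (none), 0.4-2.5% (moderate) and 0.8-6.4% (strong). With no true difference it is 0.5-1.3%. The width ratio is 1.00, 1.02-1.03 and 1.07-1.10 respectively. Coverage of the unstratified interval runs from 94.8% to 96.8%. With the stratified interval, disagreement is about 0.1-0.8% and coverage 94.6-95.2%.

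**The case against.** The strongest case for leaving the plan alone is that nothing inferential is broken. That is largely right, and it rules out three stronger readings that a reader might infer.

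- **That the test and the interval target different quantities.** Step 1 shows that the crude and weighted differences nearly coincide under 1:1 stratified blocks. The crude difference validly estimates the stated summary.
- **That precision is lost.** The sampling SD of the two estimates is the same (0.0469 and 0.0468 with strong strata). Only the reported interval can be too wide, and it errs on the conservative side.
- **That type I error is at risk.** The formal decision rests on the stratified test in the fixed sequence. A significant p-value beside an interval that includes zero is awkward to report, but it is not a false claim.

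Three further objections stand in part. The documents do not call this interval unstratified. That is an inference, because stratification is named for the test only and a stratified interval is also a normal approximation. The size rests on assumed stratum effects: SAP 4.2.4.1 groups the stratification factors with prognostic factors, but for PFS. And formal reach is limited, since ORR is tested only after OS, whose stated power is 25% at interim and 59% at final.

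None of this explains why PFS has a matched estimate and test while ORR, BOR and CBR do not.

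**Conclusion.** The point holds as a gap in specification with a modest effect on reporting. The interval for three type I error-controlled endpoints is not tied to the stratification of their test, so the two can disagree near 0.05, and the interval is conservative if the strata predict response.

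The size depends on assumptions the documents cannot settle. It ranges from no widening and at most 1.8% disagreement, if the strata do not predict response, to 7-10% widening and up to 6.4% disagreement if they predict it strongly. In the strong case nearly all disagreements are a significant test with an interval that includes zero. The case for change rests on consistency with the handling of PFS and on the very low cost.

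**What to change.** In SAP 4.3.1.2, and so by reference in 4.3.1.3 and 4.3.1.4, state that the between-arm difference and its 95% CI will be the Mantel-Haenszel-weighted stratified risk difference with a stratified variance (for example Sato), using the randomization strata as entered in IxRS. Report the unstratified interval beside it.

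This does not remove disagreement altogether, because the test uses a variance computed under the null hypothesis and the interval does not.

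The cost is one sentence and a standard programming option. Design, data collection, sample size and alpha are unchanged. SAP 1 states that the SAP supersedes the protocol's analyses, so the change can be made there.
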